#### 4.5.19 LIPID LAYER THICKNESS (TEARSCIENCE LIPIVIEW® II)

---

The participant will be seated at the LipiView® II instrument which will image and compute the lipid layer thickness (average, minimum, maximum) of the tear film. Prior to the commencement of this test, no history of seizures or discomfort with rapidly blinking lights will be confirmed.

#### 4.5.20 INSTILLATION OF EYE DROP

---

A bottle of SYSTANE® Complete will be well shaken. A couple of drops of SYSTANE® Complete will be transferred to a microtube. The participant will be asked to sit in a consulting chair with their head against the headrest and to tilt their chin up. The participant will be asked to look up and

towards their nose. The lower lid will be lowered and 15 µl of SYSTANE® Complete will be pipetted into the temporal side of the right eye. The participant will be asked to blink their eyes after the eye drop has been instilled. The process will be repeated with a new pipette tip to instill 15 µl of the eye drop into the left eye. A new microtube will be used for each participant.

## 5 MONITORING PROTOCOL ADHERENCE

Guidelines to be included on adherence to visit windows and windows around other data collection points (i.e. subjective ratings). Procedures for monitoring and reporting deviations from the windows described in the protocol.

## 6 POTENTIAL RISKS AND BENEFITS TO HUMAN PARTICIPANTS

This is a minimal risk study because of the use of marketed products, standard optometric assessments, and the use of two investigational non-invasive devices (the prototype evaporimeter and the modified swimming goggles used to measure volume).

It is possible that participants may experience temporary discomfort associated with the study procedures/devices/eye drops including: eye pain, burning and stinging, blurred vision, sandiness or grittiness, itching, irritation, redness light sensitivity, dryness, itching, crusty eyes, and foreign body sensation.

A dye (fluorescein) normally used to eye exams is being used in this study. Although rare, it is possible that participants may have an allergic reaction to the dye. This could cause discomfort to their eye.

Routine clinical procedures including visual acuity, anterior ocular health assessment, and meibography will be used.

One clinical procedure (evaporimetry) will be conducted with an investigational device consisting of a pair of modified swimming goggles containing a temperature and humidity sensor embedded in each lens of the goggle. This procedure poses minimal risk to the participants as the device is does not touch the eye and the portion of the goggle which will come in contact with the skin surrounding the eye will be cleaned with alcohol wipes between each use. Participants may experience temporary discomfort associated with petroleum jelly including; burning, stinging, irritation, blurred vision, and foreign body sensation.

One clinical procedure (measurement of volume inside the goggle) will be conducted with an investigational device consisting of a pair of modified swimming goggles containing small hole

inserted into the top of each lens. This procedure poses minimal risk to the participants as the device does not touch the eye and the portion of the goggle which will come in contact with the skin surrounding the eye will be cleaned with alcohol wipes between each use. Commercially available saline designed for use with the eyes will be inserted into the goggle. Participants may experience temporary discomfort associated with saline including; burning, stinging, irritation, blurred vision, and foreign body sensation.

One of the instruments in this study uses rapidly blinking lights to image the tear film. Participants will be asked to inform the investigator if they have a history of discomfort and seizures due to rapidly blinking lights. Participants may experience temporary discomfort including: blurred vision and light sensitivity.

Participants may not benefit directly from taking part in this study. Information from this study may help researchers come up with a new device to help others with dry eye in the future. This study may also help CORE to better understand the performance of the products being used in this study.

## 7 ADVERSE EVENTS

See CORE SOP012\_v02 for a description of all adverse events, including management and reporting.

A number of conditions may result in temporary suspension until resolution. These include corneal infiltrates, corneal staining, limbal injection, bulbar injection or tarsal conjunctival abnormalities.

## 8 DISCONTINUATION FROM THE STUDY

Participants may be discontinued at the discretion of the investigator or sponsor in consideration of participant safety or protocol compliance, or at discretion of the participant. Participants discontinued from a study will be reimbursed \$20 per hour for their active involvement in the study (including the initial screening visit). Upon discontinuing, a participant will be offered the option of their data being withdrawn from future statistical analysis. The following is a list of possible reasons for discontinuation from the study:

- Screening failure: Participants will be discontinued if they do not meet the inclusion and exclusion criteria outlined in section 4.2.3.
- Unacceptable performance with products to be used in study: Participants may be discontinued if they are unable to achieve acceptable comfort and /or vision with the study products.

- Positive slit lamp finding: Participants may be permanently discontinued from the study depending on the severity of the condition and on the judgement of the investigator.
- Adverse event: If a participant experiences an adverse event during the study they may be discontinued based on the clinical judgement of the investigator.
- Symptoms: If the participant has persistent symptoms they may be discontinued based on the clinical judgement of the investigator.
- Disinterest, relocation or illness: The participant may choose to discontinue due to reasons within or beyond their control.
- Violation of protocol or non-compliance: The participant will be discontinued if they are unable or unwilling to follow the protocol specified visit schedules and/or study procedures.
- Instillation of topical ocular medication: The participant will be discontinued if they elect to use a topical ocular medication during the study unless that topical ocular medication is prescribed for a limited duration (less than two weeks) to treat a transient condition; in this case the participant may remain an active participant (at the discretion of the investigator) after stopping topical ocular medication following resolution of the ocular condition).
- Lost to follow-up: The participant will be discontinued if they cannot be contacted and do not return for a final exit visit, and if the investigator has made a reasonable effort to contact the participant for a final study visit.
- Premature termination of the study by CORE or the Office of Research Ethics at the University of Waterloo.

A discontinuation form, stating the reason for discontinuation will be completed, which requires the signatures of both the participant and the investigator except where the participant is lost to follow-up in which case only the signature of the investigator is required.

All discontinuations including their reasons will be included in the final report.

## 9 STUDY COMPLETION AND REMUNERATION

At the last scheduled protocol visit a study completion form will be completed, which requires the signatures of both the participant and the investigator. The participants will also be provided with a letter of appreciation.

Once their involvement in the study is complete, participants will be informed about receiving feedback following study completion in the Letter of Appreciation.

Participant remuneration will be \$80 for completing the study.

## 10 STATISTICAL ANALYSIS AND DATA MANAGEMENT

### 10.1 STATISTICAL ANALYSIS

All data will be analyzed by CORE at the University of Waterloo using Microsoft Excel and statistical analysis software such as GraphPad and SPSS. Interim data analysis will be conducted after 10 dry eye and 10 non-dry eye participants have completed the study to calculate the final sample size. Descriptive statistics will be provided on information regarding baseline variables (age, sex, etc.). Table 4 lists the primary outcome variables and anticipated statistical procedures.

**Table 4: Outcome variables and anticipated statistical procedures**

Variable	Analysis	Statistical test
Tear evaporation rate	Change in relative humidity over time	Slope
Tear evaporation rate/Time	Effect of eye drop	RMANOVA Mauchly's test of sphericity Greenhouse-Geisser p values Tukey HSD post hocs Paired t-test
Tear evaporation rate/ OSDI/ Subjective ratings/ Tear meniscus height/ Non-invasive Keratograph® break up time/ Lipid layer thickness/ Area of the ocular surface	Relationship between tear evaporation rate and OSDI/ Subjective comfort, dryness, and burning/stinging/ Other tear film assessments/ Area of the ocular surface	Pearson correlation – r
Tear evaporation rate/Volume inside the goggle	Relationship between tear evaporation rate and volume inside the goggle	Spearman correlation - rho

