### 3 HYPOTHESIS

The study hypothesis is that instillation of an eye drop will result in lower tear evaporation rates compared to before the eye drop has been inserted.

The second study hypothesis is that dry eye participants will have higher baseline rates of tear evaporation compared to non-dry eye participants.

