#### 4.1 STUDY DESIGN

##### 4.1.1 OVERALL DESIGN

This is a prospective, bilateral, non-dispensing, non-randomized pilot study that will seek to successfully complete 10 dry eye and 10 non-dry eye participants who do not wear contact lenses. More participants are likely will be screened due to the potential for screen failure. The study will involve 2 scheduled visits over 2 days.

Visit 1: Screening visit

Visit 2: Data collection, including instillation of the study eye drop

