### 4.2 STUDY POPULATION

#### 4.2.1 SAMPLE SIZE CALCULATION

---

Because this is a pilot study, a sample size calculation has not been completed. Results from this study will help with sample size determination for future studies.

A *p*-value of < 0.05 will be considered statistically significant.

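### Table 4 lists both Tukey HSD and a paired t-test for the drop effect, without saying which decides, which pairs or baseline are used, or whether any adjustment applies

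*Combined protocol and SAP*

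**What the plan says.** The first hypothesis (Section 3) is that "instillation of an eye drop will result in lower tear evaporation rates compared to before the eye drop has been inserted". Section 4.4.3 schedules evaporimetry five times at Visit 2: a baseline, a repeated baseline at least 20 minutes later, and then 10, 30 and 60 minutes after the drop.

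Section 10.1 introduces the methods with "Table 4 lists the primary outcome variables and anticipated statistical procedures". The Table 4 row for the drop effect names RMANOVA, then "Mauchly's test of sphericity Greenhouse-Geisser" p values, then "Tukey HSD post hocs Paired t-test". It gives no order of precedence, list of pairs, reference baseline, adjustment or Tukey error term.

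Section 4.2.1 supplies the only error rule, a p "value of < 0.05 will be considered statistically significant", and says that "a sample size calculation has not been completed". Section 4.1.1 says the study will "seek to successfully complete 10 dry eye and 10 non-dry eye participants".

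**The concern.** Two pairwise procedures with different error properties are named for one question. Five time points give 10 pairs. Six of these are pre-drop versus post-drop, and only those bear on the hypothesis. A paired t-test uses the right error for its own pair, but several of them at 5% inflate the family-wise error. Classical Tukey spreads its protection over all 10 pairs and uses one pooled error term, which is valid only under sphericity. The same row plans for failure of sphericity, but Greenhouse-Geisser corrects the omnibus F test and leaves the Tukey error term unchanged.

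The conclusion on the first hypothesis could therefore depend on which procedure is reported. With no masking and no stated precedence, that choice can be made after the results are seen.

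**Working it through.** The plan states no power, SD, correlation or effect size, so it has no figure to reproduce.

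**Inputs from the protocol.** n = 20 (10 + 10), five times, alpha 0.05.

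**Assumptions.** Two-sided tests; one value per participant per time; both groups analysed together; normal data with equal variances; measurement times −25, −5, 10, 30 and 60 min. Two covariances are used:
- Spherical: every correlation 0.6 (epsilon 1.00).
- Non-spherical: correlation 0.6 + 0.4·exp(−gap/40 min) (epsilon 0.77).

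The error rates and powers in steps 1, 3 and 4 come from 20,000 simulated trials per scenario. The gating figures in step 2 come from 10,000, over a similar set of assumed covariances.

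**Step 1: paired t-tests at 5%, no effect.** Each test is t = mean difference / (s_d/√20), 19 df, cutoff 2.093. If the tests were independent, the chance of at least one false positive would be 1 − 0.95^m. The tests share data, so the simulated rate is lower.

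| Tests run | m | 1 − 0.95^m | Simulated |
|---|---|---|---|
| Each post-drop time vs one baseline | 3 | 14.3% | 12–13% |
| All pre-post pairs | 6 | 26.5% | 20–23% |
| All pairs | 10 | 40.1% | 28–30% |

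**Step 2: does gating on the ANOVA help?** If no time differs, requiring a significant Greenhouse-Geisser F first brings the rate for all 10 pairs down to 3.5–4.8%. If one post-drop time truly differs by a large amount, the gate is almost always open. Four times then remain equal, giving 4·3/2 = 6 true-null pairs, and the chance of a false positive among them is 20.5%. If the two baselines are merged, 3 true-null pairs remain and the rate is 12.7%.

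**Step 3: classical Tukey.** A pair is significant if |mean difference| / √(2·MSE/20) exceeds q(0.95; 5, 76)/√2 = 2.79, a per-pair level of 0.66%. Under sphericity that level applies to every pair. At epsilon 0.77 the variance of a difference, 2(1 − correlation), depends on the gap:
- Second baseline vs 10 min (15-min gap): correlation 0.6 + 0.4·exp(−0.375) = 0.875, variance 0.250.
- First baseline vs 60 min (85-min gap): correlation 0.6 + 0.4·exp(−2.125) = 0.648, variance 0.704.
- Average over the 10 pairs, which is what 2·MSE estimates: (0.315 + 0.466 + 0.598 + 0.704 + 0.250 + 0.466 + 0.642 + 0.315 + 0.570 + 0.422)/10 = 0.475.

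On each pair's own scale the cutoff becomes about 2.79·√(0.475/0.250) = 3.85 for the close pair and 2.79·√(0.475/0.704) = 2.29 for the distant one. The simulated per-pair error runs accordingly from about 0.02% to 2.5%. The family-wise rate, about 6–7%, hides this spread.

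**Step 4: power, like for like.** Second baseline vs 10 min, effect at 10 min only, standardised paired effect 0.6:

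| Procedure | Epsilon 1.00 | Epsilon 0.77 |
|---|---|---|
| Single unadjusted paired t-test | 72% | 72% |
| Holm over three comparisons | 53% | 54% |
| Pooled-error Tukey | 46% | 14% |

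In these scenarios Tukey and the unadjusted paired t-test give opposite verdicts on this comparison in about 26% of trials under sphericity and 58–59% at epsilon 0.77.

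**The case against.** The strongest reply is that the faults are inferred. The table gives method names only. It does not call the t-tests unadjusted or the Tukey error pooled. Paired t-test is in the singular and might mean one planned comparison, or a check of baseline against repeated baseline in a study that also validates the device. One pre-specified paired t-test inflates nothing. This stands: the 12–30% range describes what happens if several tests are run on the only stated rule. It is not something the plan commits to.

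A reader might also infer that Tukey generally costs much of the power for the key comparison. The documents do not support that. They name no key comparison: no primary post-drop time and no reference baseline. The loss also depends on the pair. At epsilon 0.77 with an effect at 60 min only, pooled Tukey has 61% power against 57% for Holm using the mean baseline, partly because its per-pair error is lenient there. With pair-specific standard errors Tukey reaches 48% at 10 min, not 14%. Under sphericity the like-for-like gap to Holm is 53 − 46 = 7 points. A much wider gap (46% vs 77%) appears only if Holm is given the averaged baseline and an effect at all three post-drop times while Tukey is scored on the second baseline alone.

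Finally, this is an unpowered pilot with anticipated methods, not intended for regulatory use. That lowers the stakes. It does not remove the point, because the protocol states a directional hypothesis and a significance threshold, and the results are to guide the size of later studies.

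**Conclusion.** The point holds as an undefined decision rule for the drop effect. The listing of two procedures, and the absence of a deciding rule, pairs, reference and adjustment, can be read directly from Table 4. That Greenhouse-Geisser does not repair a pooled-error Tukey test is a matter of method.

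The sizes are conditional. The false-positive rates vary little across the covariances tried. They are also similar if a group of 10 is analysed alone: under a covariance with larger post-drop SD, 12.7%, 18.8% and 28.5% for 3, 6 and 10 tests. The Tukey power figures are much less stable. The shortfall against Holm is modest under sphericity and severe only for close-in-time pairs under an assumed correlation pattern that the documents neither give nor exclude. The plan should be changed, but the case rests on the missing rule and the uneven error, not on a general loss of power.

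**What to change.** In the drop-effect row of Table 4, replace "Tukey HSD post hocs Paired t-test" with three planned comparisons: 10, 30 and 60 minutes after the drop, each against one pre-specified pre-drop reference. Test each with a paired t-test on its own difference scores, Holm-adjusted across the three at 0.05. Report all other pairs descriptively with confidence intervals. In simulation the family-wise error is then 4.2–4.9%.

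State the reference before data collection: either the mean of the two baselines or the second baseline. Neither is better throughout. For an effect at 10 min only, Holm power is 68% with the mean against 53% with the second baseline under sphericity, but 49% against 54% at epsilon 0.77.

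The cost is one table row and the loss of formal tests between post-drop times. No study procedure changes.

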#### 4.2.2 NUMBER OF PARTICIPANTS

---

Up to 60 participants will be recruited / screened using CORE records and advertising approved by the UW Office of Research Ethics, with a target of 10 dry eye and 10 non-dry eye participants completing the study. At least 20 participants will have the study product instilled at Visit 2. Informed consent will be obtained for all participants prior to their enrolment in the study.

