#### 4.2.3 INCLUSION AND EXCLUSION CRITERIA

---

A person is eligible for inclusion in the study if he/she:

1. Is at least 18 years of age and has full legal capacity to volunteer;
2. Has read and signed an information consent letter;

3. Is willing and able to follow instructions and maintain the appointment schedule;
4. Is willing to be awake for at least 2 hours before visit 2;
5. Is willing not to wear eye makeup on the day of visit 2;
6. Is willing not to use eye drops or artificial tears on the days of visits 1 or 2;
7. Group specific criteria:
  - a. Dry eye participant group: Symptoms: OSDI  $\geq$  13 and Signs: NIKBUT  $\leq$  5 s in the worst eye
  - b. Non-dry eye participant group: Symptoms: OSDI  $<$  13 and Signs: NIKBUT  $\geq$  10 s in the worst eye

A person will be excluded from the study if he/she:

1. Is participating in any concurrent clinical or research study;
2. Has any known active\* ocular disease and/or infection;
3. Has a systemic condition that in the opinion of the investigator may affect a study outcome variable;
4. Is using any systemic or topical medications that in the opinion of the investigator may affect a study outcome variable;
5. Has known sensitivity to sodium fluorescein dye;
6. Is pregnant, lactating or planning a pregnancy at the time of enrolment (by verbal confirmation at the screening visit);
7. Is aphakic;
8. Has undergone refractive error surgery;
9. Has undergone ocular surgery in the last 6 months;
10. Has punctal plugs;
11. Has a known sensitivity to Systane® eye drops (including Systane® Balance, Systane® Complete, Systane® Gel Drops, Systane® Ultra, etc.)
12. Has a known sensitivity to petroleum jelly (Vaseline);
13. Has epilepsy and/or sensitivity to flashing lights;
14. Has worn contact lenses within the past month or is planning to wear contact lenses during the study;
15. Has any physical impairment that would interfere with holding the evaporimeter;
16. Has taken part in another clinical research study involving ocular drops or treatments within the last 14 days;

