#### 4.4.2 VISIT 1: SCREENING

---

All participants who signed the informed consent letter will be assigned a study ID number. The investigator will determine participant eligibility using the inclusion and exclusion criteria. Ineligible participants will be discontinued from the study. The procedures to be performed are outlined below:

- Participants will attend the screening visit having not used any eye drops or artificial tears on the day of the visit.
- The participant will be required to read and sign an Informed Consent Form prior to enrollment. When the participant has signed the consent form, the participant will be considered to be enrolled in the study.
- Participant demographics and medical history (age, sex, current dry eye treatments, medical conditions, medications, allergies)
- Ocular Surface Disease Index (OSDI) questionnaire
- Monocular and binocular logMAR visual acuity will be recorded with high contrast letters under high illumination with spectacles (if necessary).
- Tear meniscus height (OCULUS Keratograph® 5M)
- Non-invasive Keratograph® break up time (OCULUS Keratograph® 5M)
- The investigator will confirm that the participant meets the eligibility specifications set out in the inclusion criteria to be categorized as either a dry eye or non-dry eye participant. Participants who do not meet this criteria will be discharged and will not continue with the remainder of the screening visit.
- Lipid layer thickness (EASYTEAR®view+)
- Assessment of meibomian gland secretion and expression
- Lid margin assessment
- Slit lamp biomicroscopy
- Meibography (OCULUS Keratograph® 5M)
- Anterior eye photographs of each eye will be taken with a slit lamp camera.
- Participants will practice evaporimetry measurements.
- Measurement of volume within the goggle.
- Slit lamp biomicroscopy (safety check).
- Monocular and binocular logMAR visual acuity will be recorded with high contrast letters under high illumination with spectacles (if necessary).
- The investigator will confirm that the participant meets the eligibility specifications set out in the inclusion and exclusion criteria and is eligible to continue with the study.

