#### 4.5.3 OCULAR SURFACE DISEASE INDEX (OSDI) QUESTIONNAIRE

---

The OSDI is a dry eye questionnaire that asks the participant to reflect and rate their symptoms of eye dryness in different working conditions and environments over the past week. A higher composite score indicates more severe dryness and scores can range from 0 to 100. A score of <13 will be considered asymptomatic and a score  $\geq 13$  will be symptomatic.

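### The Table 4 correlations of tear evaporation rate with OSDI and NIKBUT have no group term, although criterion 7 selects participants on those two variables; a pooled r does not estimate a population correlation

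*Combined protocol and SAP*

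**What the plan says.** Section 4.2.3, criterion 7, defines two groups. The dry eye group needs "OSDI $\geq$ 13 and Signs: NIKBUT $\leq$ 5 s in the worst eye". The non-dry eye group needs "OSDI $<$ 13 and Signs: NIKBUT $\geq$ 10 s in the worst eye". For anyone who fits neither group, section 4.4.2 says: "Participants who do not meet this criteria will be discharged and will not continue with the remainder of the screening visit". Section 4.2.2 fixes the mix, "with a target of 10 dry eye and 10 non-dry eye participants completing the study".

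Table 4 in section 10.1 lists a Pearson correlation for the "Relationship between tear evaporation rate and OSDI/ Subjective comfort, dryness, and burning/stinging/ Other tear film assessments" and for ocular surface area. Neither the table nor the rest of section 10.1 mentions dry eye status in connection with these correlations. They also do not say whether the groups are pooled, or which eye or time point is used. Section 3 hypothesises that TER is higher at baseline in the dry eye group. Section 4.2.1 adds the threshold: "A *p*-value of < 0.05 will be considered statistically significant".

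**The concern.** The two variables used to choose participants are then correlated with TER in the chosen sample. Criterion 7 removes NIKBUT values between 5 and 10 s and removes everyone whose symptoms and signs disagree. The sample is therefore two separated clusters in a fixed 1:1 ratio. A single r across both clusters combines the gap between them with whatever relation exists inside each, and the size of the gap is set by the entry rule.

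OSDI carries a second problem. Because it must agree with NIKBUT at entry, it can take on NIKBUT's relation with TER even if it has little or none of its own.

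The introduction says the study will also serve to validate the new evaporimeter, and section 4.2.1 says the results will guide the size of future studies. A reader could take a pooled r with OSDI as evidence that the device tracks symptoms, or carry it into a later calculation as if it described people in general.

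**Working it through.** The plan states no expected correlation, effect size or standard deviation, so there is no figure of its own to reproduce. The check uses the plan's entry rule with assumed distributions.

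**Inputs from the documents**
- Entry rule: OSDI at or above 13 with NIKBUT at or below 5 s, or OSDI below 13 with NIKBUT at or above 10 s (section 4.2.3).
- Group ratio 1:1, 10 + 10 (section 4.2.2).
- Threshold p < 0.05 (section 4.2.1), taken as two-sided because sidedness is not stated.

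**Assumptions (not in the documents)**
- NIKBUT log-normal, median 8 s, log SD 0.6.
- OSDI log-normal, median 13.
- TER depends on NIKBUT only, with population r = -0.30 against log NIKBUT.
- Correlation of log OSDI with log NIKBUT either 0 or -0.3.

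**Step 1: simulate and filter.** Four million people were drawn, criterion 7 was applied, and equal numbers were kept per group.

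| Correlation of TER with | OSDI–NIKBUT correlation | Population | Pooled, selected | Group-adjusted |
|---|---|---|---|---|
| log NIKBUT | 0 | -0.30 | -0.38 | -0.16 |
| log NIKBUT | -0.3 | -0.30 | -0.39 | -0.16 to -0.17 |
| log OSDI | 0 | 0.00 | 0.28 | 0.00 |
| log OSDI | -0.3 | 0.09 | 0.30 to 0.31 | 0.02 |

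On the raw OSDI scale (log SD 0.8) the distortion is smaller but still present: 0.00 becomes 0.21 pooled in the first case, and 0.08 becomes 0.23 in the second. When TER is made unrelated to both variables, every pooled r is 0.00.

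**Step 2: confirm by formula.** For two equal groups separated by dx and dy within-group SDs, with within-group correlation rw:

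pooled r = (dx·dy/4 + rw) / √[(1 + dx²/4)(1 + dy²/4)]

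In the independent case the simulated separations are dx = 2.65 for log OSDI, dx = 4.73 for log NIKBUT, and dy = 0.74 for TER.
- OSDI, rw = 0: (2.65 × 0.74/4) / √(2.756 × 1.137) = 0.490/1.770 = 0.28. All of it comes from the group gap.
- NIKBUT, magnitude, rw = 0.157: (4.73 × 0.74/4 + 0.157) / √(6.593 × 1.137) = (0.875 + 0.157)/2.738 = 0.38. The gap supplies 0.875/1.032 = 85% of the numerator.

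**Step 3: different assumptions.** Take NIKBUT with median 7.5 s and log SD 0.55, TER with a latent correlation of 0.3 with both variables, and an OSDI–NIKBUT latent correlation of -0.2 to -0.6. On the raw scales:
- NIKBUT r is -0.28 in the population, -0.40 to -0.47 pooled, and about -0.12 within groups.
- OSDI r is 0.26 to 0.27 in the population, 0.37 to 0.42 pooled, and 0.13 to 0.14 within groups.

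The group difference carries 85% to 88% of the pooled covariance for NIKBUT and about 78% for OSDI.

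**Step 4: precision at the planned size.** The critical |r| is 0.444 for 20 participants and 0.632 within one group of 10. For a partial correlation given group with 20 participants, the Fisher z standard error is 1/√(20 - 1 - 3) = 0.25. A 95% interval around zero is therefore about ±tanh(1.96 × 0.25) = ±0.45.

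**The case against.** Several stronger conclusions are tempting, and the documents do not support them.

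- **That the middle of OSDI is also excluded.** It is not. Section 4.5.3 uses one cut ("A score of <13 will be considered asymptomatic and a score" at or above it is symptomatic), and the groups meet at 13. Only NIKBUT has a gap, together with the removal of discordant pairs.
- **That the plan prescribes pooling.** Table 4 specifies neither pooling nor stratification, and it lists anticipated procedures. Pooling is the natural reading of one r with no group mentioned, but it remains an inference.
- **That the entry rule creates a correlation from nothing.** If TER is unrelated to both OSDI and NIKBUT, the pooled r is 0. The groups are defined only by those two variables, so a TER gap between them already implies an association with at least one.
- **That the rejection rates are false-positive rates.** With no within-group correlation and assumed gaps of 2 to 3 SD on X and 0.5 to 1.5 SD on TER, the pooled test at 10 + 10 rejects in 11% to 71% of runs, against about 5% for the partial correlation. Much of that is detection of the real group difference. It misleads only if read as a relation within groups, or as OSDI's own relation with TER.
- **That the group-adjusted r should replace the pooled one.** For NIKBUT the adjusted value, about -0.16, is further from the population -0.30 than the pooled -0.39, because each group covers a restricted range.
- **That every measure in the row is equally affected.** Ratings, meniscus height and lipid layer were not selection variables. They are affected only as far as they differ between groups.

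The model also uses one NIKBUT value per person. The study selects on the worst eye at Visit 1 and measures NIKBUT again at Visit 2, so the real distortion may differ. Finally, this is a pilot whose objective is TER before and after the drop, and neither hypothesis in section 3 concerns a correlation. These points limit the size and importance of the concern. They do not remove the distortion for OSDI, or the missing analysis set.

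**Conclusion.** The concern holds in a limited form. On the pooled reading, the Table 4 correlations of TER with OSDI and NIKBUT mix the dry/non-dry contrast with any within-group relation, and so do not estimate a population correlation. When TER is related to either variable, the pooled r is inflated in both models examined. The clearest case is OSDI, where a population value of 0.00 to 0.09 can appear as about 0.28 to 0.31 (0.21 to 0.23 on the raw scale) purely or mainly because entry requires agreement with NIKBUT.

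The sizes rest on assumed distributions and an assumed TER–NIKBUT correlation, since the documents give neither. The direction was the same under both sets of assumptions with a non-zero TER association. The eye-drop comparison is not affected. This is a worthwhile, inexpensive improvement to a secondary analysis.

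**What to change.** In Table 4:

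1. State the analysis set for the correlations: which participants, eye and time point, and whether the groups are combined.
2. For OSDI and NIKBUT, report a group-adjusted (partial) correlation given dry eye status, with its confidence interval, beside the pooled r. Do the same for ratings, meniscus height and lipid layer where they differ by group.
3. Show scatterplots with points marked by group.
4. State that the pooled r reflects sampling of concordant extreme groups and that the adjusted r is range-restricted, so neither estimates the population correlation.

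The cost is a few lines of text and one further analysis of data already being collected. The adjusted coefficients will usually be smaller and less often significant, and their intervals will be wide with 10 per group.
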